2. ABBREVIATIONS

Abbreviation	Definition
AE	Adverse Event
AMP	Adenosine Monophosphate
AUC	Area Under the Curve
BSA	Body Surface Area
C _{max}	Maximum Concentration
CDI	Children's Depression Inventory
COPD	Chronic Obstructive Pulmonary Disease
CRF	Case Report Form
C-SSRS	Columbia-Suicide Severity Rating Scale
CTCAE	Common Terminology Criteria for Adverse Events
FDA	U.S. Food and Drug Administration
FOCBP	Female of Child Bearing Potential
GCP	Good Clinical Practices
IB	Investigational Brochure
IC ₅₀	Half Maximal Inhibitory Concentration
ICF	Informed Consent Form
ICH	International Conference on Harmonisation
IGA	Investigator Global Assessment
I-IGA	Intertriginous IGA
IND	Investigational New Drug
IRB	Institutional Review Board
ITT	Intent to Treat
IWRS	Interactive Web Response System
LED	Light Emitting Device
μg	Microgram
MedDRA	Medical Dictionary for Regulatory Activities
mL	Milliliter
NCI	National Cancer Institute
NIH	National Institutes of Health
NOAEL	No Observed Adverse Effect Level
Ng	Nanogram

Abbreviation	Definition
NRS	Numerical Rating Score
PASI	Psoriasis Area and Severity Index
PDE-4	Phosphodiesterase 4
PHQ-A	Modified PHQ-9 for Adolescents
PHQ-8	Patient Health Questionnaire depression scale
PI	Principal Investigator
PK	Pharmacokinetics
QD	Once Daily ("quaque die")
SAE	Serious Adverse Event
TEAE	Treatment Emergent Adverse Event
T _{max}	Time to reach maximum concentration
WI-NRS	Worst Itch – Numeric Rating Scale

3. BACKGROUND AND RATIONALE

3.1. Introduction

Roflumilast is a phosphodiesterase 4 (PDE-4) inhibitor approved globally to reduce the risk of exacerbations in patients with severe chronic obstructive pulmonary disease (COPD) associated with chronic bronchitis. Roflumilast and its active metabolite, roflumilast N-oxide, are high affinity selective inhibitors of PDE-4 (a major cyclic-3',5'-adenosine monophosphate (cyclic AMP)-metabolizing enzyme), whose activity leads to accumulation of intracellular cyclic AMP. There are four different subtypes of PDE-4: PDE-4a, PDE-4b, PDE-4c, and PDE-4d, each with several isoforms (splicing variants). IC₅₀ values of both roflumilast and roflumilast N-oxide for the different PDE-4 isoforms and subtypes are mostly sub-nanomolar and single digit nanomolar ([Hatzelmann 2010](#)). The PDE-4 family of enzymes are the most prevalent phosphodiesterases in immune cells and inhibition of PDE-4 subtypes has been associated with anti-inflammatory effects in many biological systems.

The Sponsor is developing topical roflumilast in several formulations (ARQ-151 cream and ARQ-154 foam) and indications. To date, ARQ-151 cream has been evaluated in studies in psoriasis and atopic dermatitis. Additionally, two PDE-4 inhibitors have been marketed for dermatologic indications in the US and elsewhere, including OTEZLA® as an oral therapy for moderate to severe plaque psoriasis in adults and EUCRISA® as a topical therapy for mild to moderate atopic dermatitis in individuals 2 years of age and older.

Seborrheic dermatitis is a common, chronic inflammatory skin disease characterized by erythematous, scaly plaques, often with a yellowish, oily, moist, and/or greasy appearance, affecting areas of sebaceous gland abundance. Frequently involved sites include the scalp (including retroauricular areas), eyebrows, ears, nasolabial folds, eyelids, trunk, and intertriginous areas. There may be associated pruritus and/or pigmentary changes. Seborrheic dermatitis affects about 2% of the adult population ([Borda 2015](#), [Dessinioti 2013](#)) and occurs in the adolescent population as well. It may be associated with certain medications and conditions such as Parkinson's disease and other neurologic conditions, Down syndrome, and HIV infection. Seborrheic dermatitis is generally a clinical diagnosis. The exact cause of seborrheic dermatitis remains unknown. Treatment of seborrheic dermatitis may vary by location on the body involved, eg, scalp or non-scalp and periocular or not. For the scalp, anti-dandruff shampoos are often used such as anti-fungals, zinc products, selenium sulfide, salicylic acid, or tar. Topical corticosteroid products may also be used. Scalp lesions of seborrheic dermatitis can present a particular treatment challenge and form thick crusts which may not respond to topical steroids or antifungals. On non-scalp regions such as the face, topical antifungals or low potency topical corticosteroids are typically used. However, importantly, topical antifungals may demonstrate limited efficacy and topical steroids may demonstrate tachyphylaxis and cause important adverse events, particularly on the face, such as telangiectasias, acne, atrophy, rosacea, and ocular complications. Since seborrheic dermatitis is a chronic condition, treatment with topical steroids is particularly problematic due to the need for prolonged treatment duration, which may result in side effects. Other medications which have been used for seborrheic dermatitis include topical sulfur/sulfonamide products, topical calcineurin inhibitors, and oral retinoids.

Literature reports suggest that PDE-4 inhibition can be effective in the treatment of seborrheic dermatitis. Indeed, crisaborole (Eucrisa®), a PDE-4 inhibitor marketed in the U.S. for the treatment of atopic dermatitis, has been reported to be effective in the treatment of chronic nasolabial fold seborrheic dermatitis (Liu 2018). Additionally, a case report documented several subjects with recalcitrant seborrheic dermatitis successfully treated with apremilast (Cohen 2020).

Given the unmet need for new medical therapies for seborrheic dermatitis, the efficacy and safety demonstrated to date in Phase 2 studies of topical roflumilast (ARQ-151 cream) in psoriasis, and the precedent of topical anti-inflammatory agents as treatments for seborrheic dermatitis, the Sponsor is pursuing development of ARQ-154 foam for the treatment of seborrheic dermatitis. Relative to topical formulations such as a cream or gel, the foam formulation in the present study is expected to be well suited for the treatment of the scalp, where seborrheic dermatitis may predominate and be most difficult to treat. Foams have the ability to access skin lesions in hair-bearing areas and have commonly been used for treating scalp psoriasis (e.g., Olux® and Luxiq® foams) and seborrheic dermatitis (e.g., Extina® foam). In this Phase 2 open-label safety study, Arcutis will evaluate ARQ-154 foam 0.3% for the treatment of seborrheic dermatitis involving the scalp, face, and body areas.

The composition of ARQ-154 topical roflumilast foam includes minimal qualitative or quantitative changes relative to the composition of ARQ-151 topical roflumilast cream. Compared to ARQ-151, ARQ-154 foam also involves addition of a propellant that is eliminated at delivery.

[REDACTED]

[REDACTED]

3.2. Preclinical Studies

3.2.1. Toxicity Summary

Oral roflumilast is approved globally for COPD, and its safety profile is well-established. An extensive systemic toxicity program that evaluated both roflumilast and its active N-oxide metabolite in multiple species via the oral route of administration was conducted to support registration.

The previously conducted systemic toxicity program included studies to evaluate reproductive toxicity, genotoxicity and carcinogenicity, and the results of those studies are included in the labeling for oral roflumilast.

[REDACTED]

[REDACTED]

[REDACTED]

[REDACTED]

[REDACTED]

3.3. Clinical Studies

3.3.1. Topical Roflumilast Cream

The related formulation of topical roflumilast, ARQ-151 cream, has been evaluated in both psoriasis (through Phase 2b) and atopic dermatitis (Phase 2).

3.3.1.1. Psoriasis Phase 2a

ARQ-151 cream 0.5% and 0.15% have been studied in a Phase 2a study (ARQ-151-101; NCT03392168) in adult patients with mild to moderate chronic plaque psoriasis in the United States and Canada. The study included two cohorts. Cohort 1 was a single dose study to 25 cm² of psoriatic plaque(s) in 8 psoriasis subjects. Cohort 1 subjects were then enrolled, if they met entry criteria, into Cohort 2 of the study. Cohort 2 was a parallel group, double blind, vehicle-controlled study in which ARQ-151 cream 0.5%, ARQ-151 cream 0.15% or vehicle cream was applied QD for 28 days to 89 subjects with at least 0.5% BSA of chronic plaque psoriasis; area for application was not to exceed 5.0% BSA. Cohort 2 subjects had at least one target plaque of psoriasis of at least 9 cm² Target Plaque Area (TPA) in size and with a Target Plaque Severity Score (TPSS) ≥ 4 . However, all body psoriasis plaques were treated except for the face, scalp, intertriginous areas and palms/soles. Only safety and pharmacokinetics were evaluated for the single dose Cohort 1 subjects.

In the parallel group assessment (Cohort 2), the Primary Efficacy Endpoint was:

- Difference in mean percent change from baseline at Week 4 in the product of TPSS x TPA between each dose concentration level of ARQ-151 cream and vehicle control. This was assessed as a sum of up to 3 target plaques per subject.

[REDACTED]

[REDACTED]

A horizontal bar chart with 10 bars. The bars are black with white outlines. The lengths of the bars decrease from left to right. The first bar is the longest, followed by the second, and so on. The bars are set against a white background with black tick marks on the left side.

3.3.1.2. Psoriasis Phase 2b

ARQ-151 has also been evaluated in a Phase 2b study (ARQ-151-201; NCT03638258) in adult patients with chronic plaque psoriasis. ARQ-151-201 was a parallel group, double blind, vehicle-controlled study in which ARQ-151 cream 0.15%, ARQ-151 cream 0.3%, or vehicle cream was applied QD for 12 weeks to over 300 adult subjects with 2% to 20% BSA of chronic plaque psoriasis and baseline IGA of Mild or greater.

In ARQ-151-201, the Primary Efficacy Endpoint was:

- Achievement of IGA score of 'clear' or 'almost clear' at Week 6

04 November 2021

[figure not shown]
Confidential

Page 24 of 73

A 10x10 grid of 100 black rectangles. Each rectangle is positioned such that its right edge is aligned with the vertical center of the rectangle directly above it. The width of each rectangle is determined by a random value between 0.1 and 1.0. The height of each rectangle is also determined by a random value between 0.1 and 1.0. The overall effect is a pattern that tapers towards the right edge of the grid.

[figure not shown]
3.3.1.3. Atopic Dermatitis Phase 1

ARQ-151 has also been evaluated in a 15-day, open label, phase 1, PK and safety study in

3.3.1.4. Atopic Dermatitis Phase 2

A parallel group, double blind, vehicle-controlled, Phase 2 study (ARQ-151-212; NCT03916081) has recently completed and evaluated ARQ-151 cream 0.05% and 0.15% in the treatment of mild to moderate atopic dermatitis in adolescents and adults with 1.5 to 35% BSA of involvement.

Overall, ARQ-151 was found to be well-tolerated at both tested doses following once-daily topical application in subjects with mild to moderate AD. ARQ-151 showed a favorable overall safety profile at both tested doses.

3.3.2. Oral Roflumilast Tablet

Oral roflumilast (DALIRESP®, DAXAS®) has been approved globally for the treatment of COPD and has been evaluated in nine Phase III/IV randomized double-blind clinical trials ([Wedzicha 2016](#)). Overall, the safety of oral roflumilast has been well established in its targeted population of mostly middle- and upper-aged individuals who currently smoke cigarettes or have smoked them extensively in the past. Adverse events (AEs) reported with roflumilast tablets have been consistent with those expected for oral PDE-4 inhibitors. In a pooled analysis of safety data from 6-month and 1-year clinical trials (N=8630), the most common AEs were diarrhea, weight loss and nausea. Other AEs reported more frequently with roflumilast treatment than with placebo were back pain, influenza, insomnia and decreased appetite ([Michalski 2012](#), [Wedzicha 2016](#)).

In addition to the self-reported cases of weight loss in the 6-month and 1-year oral trials, clinically significant weight loss was also reported in two prospective studies that evaluated weight ([Michalski 2012](#)).

Psychiatric-related AEs were also greater in patients treated with roflumilast tablets (5.9%) compared to those treated with placebo (3.3%). The most common psychiatric-related AEs were insomnia, depression and anxiety. A small number of cases of completed suicide and suicide ideation have been reported in patients taking oral roflumilast in clinical trials and also during post-marketing experience ([Michalski 2012](#)).

The only contraindication to oral roflumilast is usage in patients with moderate to severe liver impairment (Child-Pugh B or C), where systemic levels of roflumilast may become elevated.

3.4. Rationale for Development

The development plan for ARQ-154 foam will leverage experience to date with ARQ-151 cream, which has been safe, well tolerated, and effective in Phase 2 for the treatment of psoriasis, and safe and well tolerated in a small PK study for atopic dermatitis. [REDACTED]

[REDACTED] Relative to topical formulations such as a cream or gel, the foam formulation in the present study is expected to be well suited for the treatment of the scalp, where seborrheic dermatitis may predominate.

3.4.1. [REDACTED]

[REDACTED]

[REDACTED]

[REDACTED]

The image consists of five horizontal bands of varying lengths. The top band is black with a short white segment on the right. The second band is black with a longer white segment in the center. The third band is black with a very short white segment on the right. The fourth band is black with a white segment near the bottom right. The bottom band is black with a white segment near the bottom right. The white segments are irregular and suggest a redacted or partially visible document.

3.4.2.

The safety monitoring practices employed in this protocol (i.e., physical examinations, vital signs/weight, local skin toleration assessments, hematology, serum chemistry, urinalysis, PHQ-8, modified PHQ-A, CDI-2, C-SSRS and AE questioning) are adequate to protect the subjects' safety and should detect expected AEs. The lack of nausea and vomiting seen in ARQ-151 studies to date may be related to the lack of 'peak to trough' C_{max} variation, lower C_{max} values than observed following oral administration, or bypassing of the gastrointestinal tract with topical administration

Oral roflumilast has now been used for almost a decade in the treatment of COPD exacerbations and its safety record has been well-documented. The known adverse effects of oral treatment in the COPD population (nausea, diarrhea, weight loss, psychiatric AEs; see [Section 3.3.2](#)) are monitorable, the current protocol is designed to detect these adverse events and others should they occur, and provides guidance for management, as necessary, to ensure patient safety.

4. STUDY ENDPOINTS AND OBJECTIVES

4.1. Study Objective

The objective of this study is to assess long-term safety in a multicenter, open-label, single-arm up to 52-week study in subjects with seborrheic dermatitis treated with ARQ-154 foam 0.3%.

4.2. Study Endpoints

4.2.1. Primary Endpoints

The primary endpoint will be analysis of safety monitored through application site assessments in the clinic using the method of Berger and Bowman, clinical laboratory testing, PHQ-8, Modified PHQ-A, CDI-2, C-SSRS and adverse events. Two primary endpoint analyses are planned:

- Occurrence of treatment emergent AEs (TEAEs)
- Occurrence of Serious Adverse Events (SAEs)

4.2.2. Secondary Endpoints

The secondary endpoints are related to efficacy and will include:

- Achievement of an Investigator Global Assessment (IGA) of 'completely clear' or 'almost clear', as observed over time
- A 2-grade improvement in IGA from Baseline (see [Section 7.1.1](#)) as observed over time
- 'IGA Success', defined as achievement of an IGA of 'completely clear' or 'almost clear' plus a 2-grade improvement in IGA from Baseline (see [Section 7.1.1](#)) as observed over time
- Duration of IGA Success, defined as the time from the first observation of IGA Success to the last time a subject's disease response meets the criteria for IGA Success. The duration of IGA Success for subjects who end treatment in IGA Success will be censored at the last disease assessment date
- Treatment-free interval, defined among subjects who achieve a 'completely clear' IGA and stop treatment to all lesions, as the time from attainment of a score of 'completely clear' to re-starting investigational product.

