5.4.3. Removal of Subjects from Investigational Product

A subject may discontinue from receiving the investigational product for any of the following reasons:

- Occurrence of any medical condition or circumstance that, in the opinion of the Investigator, exposes the subject to substantial risk and/or does not allow the subject to adhere to the requirements for investigational product administration as per the protocol.
- Occurrence of a treatment-emergent adverse event (TEAE) or considerable worsening of an AE that, in the opinion of the Investigator in consultation with the Medical Monitor and Sponsor, represents an unacceptable risk to the subject if he/she continues in the study. The Investigator must follow the subject until the AE resolves or satisfactorily stabilizes.
- Pregnancy.
- Subject's decision to withdraw from administration of the investigational product.
- Weight loss of >5% from Baseline if not dieting or intentionally trying to lose weight and after consultation with the Sponsor, at the Investigator's discretion.
- C-SSRS indicative of suicidal ideation.
- PHQ-8 or modified PHQ-A score ≥ 15 if determined by Investigator in consultation with a mental health professional.
- CDI-2 raw score of ≥ 32 if determined by Investigator in consultation with a mental health professional.
- Requirement for use of prohibited concomitant medication (see [Table 1](#)) after consultation with the Sponsor and Medical Monitor.
- Subject's repeated failure to comply with protocol requirements or study related procedures.

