5.4.4. Removal of Subjects from the Study

A subject may be removed from study participation for any of the following reasons:

- Subject death
- Subject's decision to withdraw from the study.
- Subject is lost to follow up. A subject will be considered lost to follow-up after three phone and three email attempts and documentation of a certified letter sent to the subject's address.
- Termination of the study by the Sponsor, FDA, or other regulatory authorities.

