7.4.5. Treatment-free Interval

The time to re-starting IP will be analyzed with the Kaplan-Meier method. The rate of subjects remaining off treatment over time will be summarized descriptively.

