- **Duration of IGA of 0** = the date of first observation of IGA > 0 - the date of first observation of IGA of 0 and stop treatment. The duration of IGA of 0 for subjects who end treatment in IGA success will be censored at the last disease assessment date. This is for subjects who achieve IGA of 0 and stop the treatment. Subjects who achieve IGA of 0 but never stop treatment will be excluded from the analysis. For subjects who achieve IGA of 0 but stop the treatment later, the duration starts from the date of stop treatment. Only the first IGA of 0 duration will be analyzed.
- **Duration of IGA of 0 or 1** = the date of first observation of IGA > 1-the date of first observation of IGA of 0 or 1 + 1. The duration of IGA of 0 or 1 for subjects who end treatment in IGA of 0 or 1 will be censored at the last disease assessment date. Only the first IGA of 0 or 1 duration will be analyzed.
- **Disease recurrence** = the date of first observation of IGA of 2 or above after achieving IGA of 0 and stop treatment - the date of first observation of IGA of 0 + 1. Only the first disease recurrence will be analyzed.
- **Treatment-free interval** = the date of re-starting study drug due to IGA score above 0 - the date of stop treatment due to attainment of score of IGA of 0 +1, among subjects who achieve a “completely clear” IGA and stop treatment to all lesions. If subjects never re-start study drug after stopping treatment, the treatment-free interval is censored at the end of study date. Only the first treatment-free interval will be analyzed.
- **Weight of IP (g)** = dispensed can weight – returned can weight.
- **BMI (kg/m²)** = (weight in kg)/[(height in cm/100)²]. Day 1 height will be used for BMI derivation upto Week 24. For visits including week 24 through week 36, week 24 height

will be used to derive BMI. Week 52 BMI is derived using the height and weight collected at the same visit. This derivation is applied since height is not collected at all visits.

- **BMI Categories:**

- Underweight: $BMI < 18.5$
- Normal: $18.5 \leq BMI \leq 24.9$
- Overweight: $25.0 \leq BMI \leq 29.9$
- Obese: $BMI \geq 30.0$

- **WI-NRS 4-point reduction** = achievement of a 4-point reduction in WI-NRS pruritus score post-baseline compared to baseline, calculated only for subjects with a pruritus score of ≥ 4 at baseline.
- **Itch-free state** = achievement of in WI-NRS of 0 or 1.

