7.1. Subject Disposition

Disposition summary will include tabulation of the number of subjects who enrolled into each cohort/group, the number of subjects who received treatment, number of subjects who completed the study, number of subjects who prematurely discontinued the study, the reasons for

discontinuation from the study overall and due to COVID-19 disruption, and number of subjects in each analysis population as identified in Section 5.

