Similar analysis from primary baseline will be performed.

Treatment Free Interval

Time to restarting study drug (treatment free interval), defined as time from when subject achieves disease clearance (IGA of 0) and stop treatment to all lesions to time when treatment restarts due to IGA of 2 or above, will be calculated and summarized in the same manner as duration of IGA success. The number (%) of subjects who achieved disease clearance (IGA of 0) and stopped treatment will be presented as well. If the subjects never restart the study treatment after achieving IGA of 0, the subject will be censored at the end of study date.

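### Treatment-free interval: a subject who relapses off IP and switches to another seborrheic dermatitis therapy is still counted as treatment-free to the end of study

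*Protocol*

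**What the plan says.** **Definition.** Protocol 4.2.2 names the treatment-free interval as a secondary endpoint. Among subjects who clear and stop treating all lesions, it is defined "as the time from attainment of a score of 'completely clear' to re-starting investigational product". Protocol 7.4.5 adds: "The time to re-starting IP will be analyzed with the Kaplan-Meier method". Neither section gives a censoring rule.

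**Censoring.** SAP 6.1.7 supplies the rule: "If subjects never re-start study drug after stopping treatment, the treatment-free interval is censored at the end of study date". SAP 8.2.1 repeats it: "If the subjects never restart the study treatment after achieving IGA of 0, the subject will be censored at the end of study date". The SAP does not define the end of study date for this endpoint. The nearest text is in SAP 6.1.8, on imputing partial end dates, where a subject's last study date is last contact, completion or early termination.

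**Removal from IP and from the study.** Protocol 5.4.3 lists reasons why a subject may come off IP, among them "Requirement for use of prohibited concomitant medication". Protocol 5.4.4 is a separate list, opening "A subject may be removed from study participation for any of the following reasons". It covers death, the subject's decision, loss to follow-up and termination of the study. Coming off IP and using a prohibited therapy are not on it.

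**Restart trigger.** Protocol 4.2.2 counts any restart. SAP 6.1.7 counts a restart because IGA is above 0. SAP 2.2.1.2 and 8.2.1 run to the "time when treatment restarts due to IGA of 2 or above".

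**Disposition.** SAP 7.1 tabulates "number of subjects who completed the study, number of subjects who prematurely discontinued the study", with reasons for leaving the study. It has no row for stopping IP.

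**The concern.** Take a subject who clears, stops IP, relapses, and uses a medicated shampoo, topical antifungal or topical corticosteroid from protocol Table 1 rather than restarting IP. Nothing in protocol 5.4.4 obliges that subject to leave the study. IP is never restarted, so under SAP 6.1.7 and 8.2.1 the interval runs event-free to the end of study. The subject is on treatment and is counted as treatment-free, which contradicts the endpoint's own name.

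Such subjects stay in the Kaplan-Meier risk set without contributing an event, so they can only raise the curve. They are also the ones whose disease came back. At stake is a named secondary endpoint that will be read as time off therapy after clearance.

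SAP 7.1 has a related, smaller gap. A subject who comes off IP for a reason in protocol 5.4.3 that is not coded as an adverse event, and who stays in the study, appears in no disposition row for that stop.

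**Working it through.** The plan has no figure to reproduce. SAP 3.2 says that the sample size rests on no power or precision calculation, and neither document gives a clearance rate, a restart rate or a rate of IP discontinuation. What can be checked is the direction of the error and its size over a range of assumptions.

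**Assumptions (none from the documents).**
- m is the median time to IP restart if nobody switched, with constant restart hazard λ = ln 2 / m.
- c is a constant hazard of switching therapy or stopping IP permanently during the interval, with the subject staying in the study.
- f = c / (λ + c) is the share of stoppers whose switch or stop would come before restart.

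**Direction.** Censoring at the switch or stop estimates exp(−λt). The SAP rule estimates 1 − (1 − f)·(1 − exp(−λt/(1 − f))), which is never lower.

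**Median.** Setting the SAP curve to 0.5 gives t = m·(1 − f)·log2[(1 − f)/(0.5 − f)]. The ratio t/m does not depend on m. For f = 10% it is 0.9 × log2(0.9/0.4) = 0.9 × 1.170 = 1.053.

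With m = 120 days, censoring at the switch or stop gives 0.379 off treatment at 168 days and 0.144 at 336 days. The SAP rule gives:

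| f | Median (days) | Excess | Off treatment at 168 days | At 336 days |
|---|---|---|---|---|
| 2% | 121.1 | +0.9% | 0.384 | 0.155 |
| 5% | 122.9 | +2.4% | 0.392 | 0.173 |
| 10% | 126.4 | +5.3% | 0.406 | 0.204 |
| 15% | 130.6 | +8.8% | 0.421 | 0.237 |
| 20% | 135.8 | +13.2% | 0.438 | 0.271 |

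**Extreme case.** If the affected subjects could never restart from day 0, the factor (1 − f) outside the logarithm drops out and the ratio becomes log2[(1 − f)/(0.5 − f)]. That gives +8%, +17% and +28% for 5%, 10% and 15%.

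**Simulation check.** This used 20,000 subjects, clearance at Week 4, 12, 24 or 36, an administrative end at Week 52, m = 120 and f = 10%. The Kaplan-Meier medians were:
- 126 days under the SAP rule with subjects staying in the study;
- 119 with censoring at the switch or stop;
- 120 if subjects leave the study within 14 days and are censored then;
- 107 if the switch or stop counts as the end of the interval.

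The last figure answers a different question, time to restart or switch, whose analytic median is m(1 − f) = 108 days.

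**The case against.** The case against has several parts.

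- **The situation may be rare.** Protocol Table 1 therapies are prohibited, and subjects must contact the site before restarting IP (protocol 5.6.3 and 6.5). Deviations are reviewed and listed (SAP 7.5). No document gives a frequency. This stands, and it is why the size is open.
- **Follow-up to Week 52 after coming off IP is not stated.** The documents permit it, but no visit schedule is given for such subjects, and protocol 6.1.10 and 6.6.4 limit adverse-event follow-up to one month after treatment. If the end of study date means each subject's own last date, those who leave are censored on leaving and little bias remains. This also stands. The SAP does not say so for this endpoint, however, and the rule still fails for those who stay.
- **Other endpoints cover remission.** Time to disease recurrence and duration of IGA 0 use IGA scores. They help only in part, since they too have no rule for other therapy.
- **The remedy is a choice of estimand.** In the example, counting the switch as an event moves the median more (126 to 107) than censoring at it (126 to 119). That is fair, and it is a reason to state the choice and show both.

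Three stronger readings are tempting, and the documents do not support them.

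- A reader might infer that everyone permanently off IP is mishandled. A subject off IP and on nothing else is still off treatment, which is what protocol 7.4.5 summarises.
- A reader might take 8% to 28% as the likely error. That needs the affected subjects to be unable to restart from day 0, whereas they are at risk of restart until they switch or stop.
- A reader might infer that the report will not show who stopped IP. SAP 9.1 and 9.1.1 tabulate adverse events leading to drug withdrawal separately from those leading to study withdrawal, and protocol 7.2.1 lists discontinuations from IP due to adverse events. Only stops not coded as adverse events lack a row.

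**Conclusion.** The concern holds for subjects who switch to another seborrheic dermatitis therapy and remain in the study. The SAP's written rule counts them as treatment-free while they are treated, and the error runs in one direction only.

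Its actual size cannot be derived from the documents. Measured against censoring at the switch or stop, the median is about 1% to 13% too long for assumed shares of 2% to 20%. This rests on constant hazards and on continued follow-up after the switch or stop. The share f pools switches with permanent stops, so the part due to switching alone is no larger. With prompt exit from the study and censoring on exit, the error is near zero.

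The endpoint is secondary and descriptive, in a single-arm study with no inferential analysis. The change should be made because the rule gives a wrong result and is cheap to correct. No main conclusion of the study depends on it.

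**What to change.** **SAP 6.1.7 and 8.2.1**
1. End the treatment-free interval, as an event, at the earlier of IP restart or first recorded use of a protocol Table 1 therapy given for seborrheic dermatitis. Name the protocol table explicitly, because Table 1 in the SAP is the schedule of events.
2. Define the end of study date as the subject's own date of completion, early termination or last contact.
3. Report the number of subjects whose interval ends through other therapy, and keep the current rule as a sensitivity analysis.
4. Reconcile the restart trigger across protocol 4.2.2, SAP 2.2.1.2, SAP 6.1.7 and SAP 8.2.1. As written, a subject who restarts at IGA 1 has an event under some of these texts. Under the others that subject has no event and is not a never-restarter either.
5. Optionally, add a sensitivity analysis that censors subjects on no other therapy at permanent IP discontinuation. It must use the date of the decision to discontinue. The last application date would censor subjects who had already stopped for clearance at about day 0. The documents do not show that a decision date is collected, so this needs checking first.

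**SAP 7.1**

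Add rows for premature discontinuation of IP, with the protocol 5.4.3 reasons, beside the study-level rows.

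**Cost.** SAP wording and minor programming. Concomitant medications are reviewed at every clinic and phone visit (protocol 1.3 and 6.1.11), and duration and reason for use are recorded (protocol 5.5.1). The reported interval will be somewhat shorter.
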